14. DATA MANAGEMENT SYSTEM

To provide data collection we will utilize the ONCORE database for both accrual entry and trial data management. ONCORE is a Clinical Trials Management System designed with the capability for: study setup, activation, tracking, reporting, data monitoring and review and eligibility verification. It is housed on secured servers maintained at the University of Florida Health Science Center on the University of Florida campus. The e- CRFs on ONCORE are 21 CFR part 11 compliant, and all users are assigned password protected user accounts.

15. STATISTICAL CONSIDERATIONS

Statistical analyses will be conducted by the study biostatistician using SAS v9.1 (SAS Institute, Cary, NC).

Routine data listing or tabulation review during the study conduct will be performed to identify missing data, anomalies, outliers, etc. Missing data will generally not be imputed. Baseline is defined as the last non-missing measurement for a variable prior to the initial dose of any investigational product.

Descriptive statistics will be provided to summarize demographic and baseline characteristic parameters. Categorical data will be summarized as frequency and its corresponding percentage. For continuous data, frequency (n), mean, standard deviation, median (as appropriate), minimum, and maximum will be provided for each parameter.

15.1 Sample Size Determination

This is a pilot study and due to the limited number of potential patients who may present with this rare disease, a sample size of 10 patients was chosen based on availability.

15.2 Analysis of the Primary Endpoint

PFS is defined as the time from treatment start to the first of either (1) documented disease progression or (2) death as a result of any cause. Patients who did not progress nor die or are lost to follow-up will be censored at the day of their last objective tumor assessment. The Kaplan-Meier method will be used to estimate the median PFS time, together with a 95% confidence interval (CI). PFS will be determined by MRI imaging.

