8. STUDY ASSESSMENTS AND PROCEDURES

| | Baseline | Day -5 to +14 or Discharge (Daily unless stated otherwise) | After Discharge: Weekly until stable | Day 30 | Day 100 | Every 3 – 6 months | 1 Year | Yearly until 5 years from transplant |
|---|----------|--|--------------------------------------|--------|---------|------------------------------|--------|--------------------------------------|
| H&P with VSS | X | X | X | X | X | X | X | X |
| Performance Status | X | X | X | X | X | X | X | X |
| AE Assess | | X | X | X | X | X | | |
| ECG, ECHO, and/or MUGA Scan, and/or Cardiac MRI | X | | | | | | X | yearly if abnormal |
| PFT's | X | | | | | | X | yearly if abnormal |
| CBC & Diff | X | X | X | X | X | X | X | X |
| PT/PTT/INR | X | | | | | | | |
| BMP, Mg, Phos | X | X | X | X | X | X | X | X |
| LFT's, LDH | X | Weekly | X | X | X | | X | X |
| TFT's (TSH, free T4) | X | | | | | | X | X |
| IgG | X | | | X | X | | X | |
| CD4, CD8 | | | | X | X | | X | |
| CT or MRI Primary / Metastatic Site | X | | | | X | X (at 6 months and 9 months) | X | X |
| PET Scan | X | | | | X | X (at 6 and 9 months) | X | X |

| | | | | | | | | |
|-----------------------------|---|--|--|--|--|--|---|--|
| Audiogram | X | | | | | | X | |
| Creatinine Clearance or GFR | X | | | | | | | |
| DEXA Scan | | | | | | | X | |

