10. EFFICACY ASSESSMENTS

- 10.1.** Tumor response will be assessed using MRI/CT/PET imaging of the primary site and known metastatic sites.
- 10.2.** Measureable disease: the presence of at least one measurable lesion that can be accurately measured in at least one dimension (the longest diameter) and with a minimum size of 10 mm by CT or MRI scan.
- 10.3.** Non-measurable lesions: all other lesions including leptomeningeal disease, pleural/pericardial effusion, and blastic bone lesions.
- 10.4.** All measurements should be recorded in metric notation, using a ruler or calipers using the same method of assessment to characterize each identified and reported lesion at baseline and during follow-up.
- 10.5.** All baseline evaluation should be performed as close as possible to the initiation of conditioning treatment and not more than 30 days before conditioning treatment begins.
- 10.6.** Response Criteria include:

11. Response Criteria for Patients with Solid Tumors

This study will use a modified version of the Response Evaluation Criteria in Solid tumor (RECIST) from the NCI to evaluate disease response. The modifications will include volumetric measurement of the primary NPC and assessment of associated adenopathy. Measurable and non-measurable metastatic foci in the lungs, bones and liver will be evaluated as per RECIST.

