15.3 Analysis of Secondary Endpoints

The objective RR is equal to the proportion of patients achieving a best overall response of partial or complete response (CR + PR), according to imaging from the start of the treatment until disease progression/recurrence. Clinical benefit rate is equal to the objective RR plus the proportion of patients attaining stable disease (CR + PR + SD). Patients who do not have a tumor response assessment for any reason will be considered nonresponders and will be included in the denominator when calculating the response rate. The number of patients achieving a response will be divided by the total of patients treated to yield the proportion responding. Exact confidence bounds (95% CI) will be calculated.

Overall survival is defined as the time from the date of treatment start to the date of death from any cause. If the patient is alive at the end of the follow-up period or is lost to follow-up, OS will be censored on the last date the patient is known to be alive. OS will be evaluated by the Kaplan-Meier method and a 2-sided 95% CI will be provided for the median OS.

Time to progression (TTP) for responders only is measured from the time measurement criteria are first met for CR/PR (whichever is first recorded) until the first date that the criteria for PD are met, or death. TTP will be

estimated with the Kaplan-Meier method; a 90% CI will be provided for the median TTP. Patients who do not relapse are censored at the day of their last objective tumor assessment. The freedom from metastasis rate is defined below and will be calculated based on an intention to treat principle. Determination of the anatomic site of first failure for patients with PD will be recorded and analyzed. Duration of response is also defined below.

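### Section 15.2 ties PFS to MRI, but no scheduled visit requires an MRI, so progression in a patient followed by CT has no settled date for the primary endpoint

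*Combined protocol and SAP*

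**What the plan says.** Section 15.2 defines a PFS event as the first of "1) documented disease progression or (2) death as a result of any cause", with no modality named. Patients without an event "will be censored at the day of their last objective tumor assessment", again with no modality named. The section then ends: "PFS will be determined by MRI imaging".

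The other sections on imaging are wider:

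- The Section 8 schedule has one row for cross-sectional imaging, "CT or MRI Primary / Metastatic Site", and a separate PET row marked at the same visits.
- Section 10.1: "Tumor response will be assessed using MRI/CT/PET imaging of the primary site and known metastatic sites".
- Section 10.2 defines a measurable lesion "with a minimum size of 10 mm by CT or MRI scan".
- Section 10.4 requires measurements "using the same method of assessment to characterize each identified and reported lesion at baseline and during follow-up".
- Section 15.3 runs time to progression, for responders only, "until the first date that the criteria for PD are met, or death". Section 15.5 ends duration of response at objectively documented recurrence or progression, or at death. Neither is limited to MRI.

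**The concern.** The primary endpoint names a scan that the schedule never requires. A patient imaged by CT at every visit follows Sections 8 and 10 exactly, yet has no MRI for the progression component of PFS. The plan does not say what to do with that patient's CT findings.

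If the last sentence of 15.2 is applied as a rule, a clear progression on CT may not count, or may count only at a later date, while the same scan ends time to progression or duration of response for a responder. One patient could then carry different progression dates for different endpoints. If the censoring rule is also read as MRI-based, a CT-followed patient who never progresses loses follow-up time that was in fact observed. Two analysts could produce different PFS curves from the same data, each with support in the text.

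**Working it through.** **Step 1: count the visits.** Section 8 marks the CT or MRI row at baseline (1), Day 100 (1), months 6 and 9 (2), year 1 (1) and yearly to year 5, that is years 2, 3, 4 and 5 (4). The total is 1 + 1 + 2 + 1 + 4 = 9. Either modality satisfies each visit, so MRI is required at 0 of 9.

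**Step 2: follow one compliant patient.** Suppose the lesions are measured by CT at baseline, as 10.2 allows. Section 10.4 then keeps those lesions on CT, and Section 8 is met by CT at every later visit. The patient has 9 acceptable scans and no MRI. Section 15.5 lets the PI decide in rare cases where progression could not be clearly assessed. An unambiguous progression on CT is not such a case, so that clause does not fill the gap.

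**Step 3: size of one patient.** The plan gives no PFS figure to reproduce. Planned enrolment is 10 (5.2). The Kaplan-Meier drop at an event is S/n, where S is the estimate just before the event and n the number at risk. With no earlier censoring S = n/10, so the drop is 1/10. Earlier censoring lowers n without lowering S, so the drop can only be larger. One progression counted or not counted is therefore a step of at least 10 percentage points at its date.

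**Step 4: illustrations on assumed data.** Ten patients, no ties and no other censoring. In (a) and (b) the fifth patient progresses on CT after four counted events, when S = 6/10 = 0.60. If that progression is counted, S = 0.60 × 5/6 = 0.50, and after the next patient's event 0.50 × 4/5 = 0.40.

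- (a) Dated late: the patient stays at risk until after the next patient's event. S is 0.60 at the CT date, then 0.60 × 5/6 = 0.50. The gap is 10 points at both times, and PFS looks longer.
- (b) Not counted, with the patient censored at that CT: S is 0.60, then 0.60 × 4/5 = 0.48. The gap is 10 points, then 8, and PFS looks longer.
- (c) A CT-followed patient who never progresses, under a consistent MRI-only reading: with no MRI after treatment start, assume censoring at treatment start (the plan states no convention). After five events among the other nine, S = 4/9 = 0.44. With the patient kept at risk, S = 5/10 = 0.50. The gap is about 6 points, and PFS looks shorter.

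The cases pull in opposite directions, and the documents do not say how many patients of each kind to expect.

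**The case against.** The best defence is that this is loose wording and not a contradiction. Section 15.2 does not say that MRI is the only admissible scan, and its event definition has no modality limit. Section 8 permits MRI at every visit, so a site that always chooses MRI satisfies both sections. The combined row for primary and metastatic sites could mean MRI at one site and CT at another, and 10.4 does not forbid an additional MRI. No passage says that anyone will be followed by CT alone. The study is also a pilot of 10 patients chosen by availability, with no comparator, hypothesis test or PFS threshold.

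Much of this stands, and it rules out three stronger readings that a reader might infer:

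- That the plan expressly excludes CT progressions. It does not; the text is ambiguous.
- That a patient would be censored at the very CT that shows progression, as in (b). This needs an MRI rule for events and an any-scan rule for censoring. The censoring sentence also covers patients who did not progress, and one with clear CT progression is hard to place there.
- That PFS is biased upward. Missed or late progressions do lengthen it, but early censoring of CT-followed non-progressors can shorten it, as in (c).

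The defence does not remove the gap. The sentence is the only modality rule given for the primary endpoint, no passage requires the scan it relies on, and none says how progression on CT is handled for PFS.

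**Conclusion.** The concern holds as a gap between the primary-endpoint definition and the imaging schedule. MRI is required at 0 of 9 time points, and a fully compliant CT-followed patient has no scan to which the MRI sentence in 15.2 can be applied. Only the progression component is affected, because death from any cause remains an event.

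The net effect on PFS has no derivable direction or size. It depends on how many patients are followed by CT, how many of those progress, and which reading the analyst adopts, none of which the documents give. What can be said is that at N = 10 one progression counted or not is a step of at least 10 percentage points at its date, and 15.2 commits to a median with a 95% confidence interval. That is enough to warrant settling the wording before analysis. Confidence is high for the mismatch and limited for any particular consequence.

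**What to change.** Delete the MRI sentence in 15.2 and put in its place:

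> Progression is determined by the protocol response criteria on the imaging specified in Sections 8 and 10 (same method per lesion as at baseline), or by other documented progression such as tissue, and is dated at the first assessment meeting the criteria. The same progression date is used for PFS, TTP and duration of response, and PFS is censored at the last such objective tumor assessment.

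State before analysis whether a PET-only finding counts as progression, consistent with 10.1; either answer can be written in. Tissue is included because 15.2 speaks of documented progression generally and 5.5.1.2 already accepts tissue diagnosis of recurrence at entry. The edit settles modality and dating only and takes the response criteria in Sections 10 and 11 as given.

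Requiring MRI in Section 8 wherever PFS is assessed would also reconcile the passages, but it would change the imaging schedule.

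The cost is a few sentences of text, using scans already scheduled. The PFS estimate may move in either direction relative to an MRI-only reading.

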15.3 Analysis of Secondary Endpoints

The objective RR is equal to the proportion of patients achieving a best overall response of partial or complete response (CR + PR), according to imaging from the start of the treatment until disease progression/recurrence. Clinical benefit rate is equal to the objective RR plus the proportion of patients attaining stable disease (CR + PR + SD). Patients who do not have a tumor response assessment for any reason will be considered nonresponders and will be included in the denominator when calculating the response rate. The number of patients achieving a response will be divided by the total of patients treated to yield the proportion responding. Exact confidence bounds (95% CI) will be calculated.

Overall survival is defined as the time from the date of treatment start to the date of death from any cause. If the patient is alive at the end of the follow-up period or is lost to follow-up, OS will be censored on the last date the patient is known to be alive. OS will be evaluated by the Kaplan-Meier method and a 2-sided 95% CI will be provided for the median OS.

Time to progression (TTP) for responders only is measured from the time measurement criteria are first met for CR/PR (whichever is first recorded) until the first date that the criteria for PD are met, or death. TTP will be

estimated with the Kaplan-Meier method; a 90% CI will be provided for the median TTP. Patients who do not relapse are censored at the day of their last objective tumor assessment. The freedom from metastasis rate is defined below and will be calculated based on an intention to treat principle. Determination of the anatomic site of first failure for patients with PD will be recorded and analyzed. Duration of response is also defined below.

15.4 Analysis of Safety Data

Safety analyses will be performed on all patients who receive any dose of study medication. Adverse events that occur more than 30 days after the administration of the last dose of treatment will not be included.

The safety and tolerability of study drug is determined by reported AEs, physical examinations, laboratory tests, and ECGs. All patients will be assessed regularly for potential occurrence of AEs from the time that treatment starts until 60 days after the last dose of study therapy. AEs will be summarized with the incidence and percentage of patients with at least one occurrence of a preferred term (according to the most severe NCI-CTCAE Version 4.0 grade) will be included. The number of AEs reported will also be summarized. Causality (relationship to study drug) will be summarized separately. Duration of AE will be determined and included in listings along with action taken and outcome. Laboratory AEs will be monitored from the time that treatment starts until 30 days after the last dose of study therapy. Laboratory results will be classified according to NCI-CTCAE, Version 4.0. Incidence of laboratory abnormalities will be summarized; laboratory results not corresponding to an NCI-CTCAE Version 4.0 term will not be graded. Laboratory toxicity shifts from baseline to worst grade will also be provided. The results from physical examination and vital sign measurement will be tabulated. Descriptive statistics will be provided as appropriate.

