12.6 SAE Reporting: All grade 3 non-hematologic SAE's must be collected, including those thought to be associated with protocol-specified procedures. Collection of all SAEs must continue for 60 days after the last administration of the investigational products. All SAE's must be reported to UF-IRB-01 within 5 working days.

12.7 Laboratory Test Abnormalities – all laboratory test results captured as part of the study should be recorded following institutional procedures. In general, non-clinically significant laboratory deviations are not considered adverse events. Laboratory deviations which require treatment delay, modification or discontinuation or are otherwise clinically significant should be reported as adverse events.

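### Section 15.4 drops adverse events after day 30 from the safety tables, although AEs are assessed and SAEs collected to day 60

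*Combined protocol and SAP*

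**What the plan says.** Section 15.4 bases the safety analyses on everyone given any study medication and then limits them in time: "Adverse events that occur more than 30 days after the administration of the last dose of treatment will not be included".

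Its next paragraph states that patients are "assessed regularly for potential occurrence of AEs from the time that treatment starts until 60 days after the last dose of study therapy". The planned outputs follow, with no time limit attached to them:

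- Incidence by most severe grade: "AEs will be summarized with the incidence and percentage of patients with at least one occurrence of a preferred term".
- Event counts: "The number of AEs reported will also be summarized".
- Relationship to treatment: "Causality (relationship to study drug) will be summarized separately".
- Listings: "Duration of AE will be determined and included in listings along with action taken and outcome".

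Laboratory events have their own, shorter window: "Laboratory AEs will be monitored from the time that treatment starts until 30 days after the last dose of study therapy".

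On the collection side, Section 12.6 states: "Collection of all SAEs must continue for 60 days after the last administration of the investigational products". The Section 8 schedule marks AE assessment daily from Day -5 to Day +14 or discharge, weekly after discharge until stable, at Day 30, at Day 100, and every 3-6 months.

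**The concern.** Aim 3.2 is to evaluate the toxicity of the conditioning regimen with autologous transplant. It is one of only two specific aims, and 15.4 is the analysis section that serves it. The 30-day sentence covers all AEs, SAEs included. An event that begins in the second month after treatment is recorded and sent to oversight, yet is absent from the trial's own account of incidence, worst grade, number of events and causality.

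The sharpest case is a fatal event that begins around Day +40. The death would count in PFS (15.2) and OS (15.3). The event, its grade and its attribution to treatment would not appear in the safety tables, so those tables would not show a treatment-related death. The documents give no reason for analysing a shorter period than is collected. They provide no separate summary of days 31-60, and it is unclear whether the AE listings keep those events.

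**Working it through.** The plan states no figure to reproduce. The check sets the windows side by side and counts days.

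**Inputs**

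| Item | Value | Source |
|---|---|---|
| Analysis cut-off for AEs | 30 days after last dose | 15.4, first paragraph |
| AE assessment | treatment start to 60 days after last dose | 15.4, second paragraph |
| SAE collection | 60 days after last administration | 12.6 |
| Laboratory AE window | 30 days after last dose | 15.4, second paragraph |
| Conditioning chemotherapy | Day -5 to Day -2 | schedule table, 5.5.4 |
| Stem cell infusion | Day 0 | schedule table, 5.5.4 |
| Post-treatment care counted within the treatment period | 6-8 weeks = 42-56 days | 5.3 |
| Planned patients | 10 | 5.2, 15.1 |

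**Day counts.** Neither 12.6 nor 15.4 defines the last dose, so the count is made for each plausible anchor. The assessment window runs from Day -5, through Day 0, to the anchor plus 60 days. Its length is 5 + 1 + last day.

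| Last dose taken as | 30-day cut-off | 60-day end | Days excluded | Whole window | Share excluded |
|---|---|---|---|---|---|
| Day -2 (last scheduled chemotherapy) | Day +28 | Day +58 | +29 to +58 = 30 | 5 + 1 + 58 = 64 | 30/64 = 47% |
| Day -1 (if the 17-hour ifosfamide infusion ends then) | Day +29 | Day +59 | +30 to +59 = 30 | 5 + 1 + 59 = 65 | 30/65 = 46% |
| Day 0 (stem cell infusion) | Day +30 | Day +60 | +31 to +60 = 30 | 5 + 1 + 60 = 66 | 30/66 = 45% |

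On every anchor, the share of the post-dose period excluded is 30/60 = 50%.

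**Against the schedule.** On the Day -2 anchor the cut-off falls two days before the scheduled Day 30 assessment, so onsets on Days +29 and +30 found at that visit are excluded. On the Day 0 anchor none are. On any anchor the cut-off falls inside the 42-56 days of post-treatment care that 5.3 counts as part of treatment.

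**Effect on the tables.** Each excluded AE lowers the event count by one. The incidence table changes only in some cases. If a late AE has a preferred term that no patient had within the window, 1/10 (10%) becomes 0/10. If it repeats a term already recorded in the same patient at the same or a higher grade, no incidence entry changes.

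**The case against.** An analysis window may legitimately be shorter than a collection window, and the plan can be carried out as written: one sentence governs analysis, the others collection. The consequences are bounded. SAEs to day 60 go to the IRB (12.6), the monitoring committee reviews all SAEs and toxicity reports (Section 13), deaths count in PFS and OS, and the plan states no safety test or stopping threshold that uses the tables. The percentages count calendar days, not events. The excluded days are also the thinly observed ones, since a patient stable by Day 30 has no AE visit named in the schedule before Day 100. A longer window may also take in events caused by progression or later treatment. Finally, keeping 30-day tables and adding a table for days 31-60 would close the same gap.

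Much of this stands as qualification. The plan is executable, the shares are shares of time, and ascertainment after discharge is sparser. It does not remove the problem. Nothing says the shorter window is intended. If it is, it still leaves out data already collected on a stated aim. Review by oversight bodies is not the trial's own summary of toxicity. Events due to progression or later treatment are a matter for the causality summary that 15.4 already plans, not a reason to omit them. A second table for days 31-60 would also work, but the plan does not contain one.

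**Conclusion.** The point holds and should be fixed. As written, 15.4 excludes from the safety summaries every AE that occurs more than 30 days after the last dose. That is 30 of 60 post-dose assessment days (50%), or 45% to 47% of the whole assessment window, depending on which day counts as the last dose. The figures assume that treatment starts on Day -5 and that the schedule is followed. They describe time, not events: no late-event rate is given, so neither the number of AEs lost nor any bias in the toxicity rates can be computed. Efficacy endpoints and oversight reporting are untouched. The damage is confined to the descriptive safety tables, but those tables are the analysis that serves aim 3.2.

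**What to change.** - In 15.4, delete the 30-day exclusion and state: *AEs with onset from treatment start through 60 days after the last dose are included in the summary tables; AEs recorded later at scheduled visits are listed separately.* The separate listing is one workable option; the documents do not require it.
- Use one definition of last dose in 12.6 and 15.4: the last chemotherapy dose given. The schedule table in 5.5.4 already uses the term in that sense for the interval to stem cell infusion.
- State that the 30-day laboratory window applies only to the routine tabulation of graded results and shifts, and that a clinically significant laboratory deviation reported as an AE under 12.7 follows the 60-day rule.
- Footnote the AE tables to say that assessment is daily in hospital and less frequent after discharge.

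The cost is three or four sentences in 15.4 and one shared definition. No new AE or SAE collection is needed, and no new laboratory tests: Section 8 already schedules blood counts and chemistry weekly after discharge until stable, at Day 30 and at Day 100. The price is that reported AE rates may look less favourable.
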